**Passive range of motion (ROM) or passive stretching for the control group:**

**Participants and caregiver will be trained on passive ROM.** A trained caregiver sits on a stool and cups participant's leg proximal to the ankle joint and move it from 90-degrees of knee flexion to full knee extension. The leg will be maintained in extension for 5 sec and returned to flexion for 5 sec. The passive actions is repeated in the manner described in the RT protocol; 10 reps on the right leg followed by 10 reps on left leg for a total of 4 sets x 10 reps. This will help to balance the design between the two groups and training will be conducted twice weekly.

**Home Video Telehealth Service:** Home exercise training will be conducted using Video Telehealth services, (known as, VA Video Connect (VVC)), under guidance from the Office of Connected Care with management and oversight from the VISN Telehealth Manager and Facility Telehealth Coordinator. The telehealth Program is located in the SCI&D service. The applicant is versed in the use of Telehealth for patient care as this has been the primary mode of patient evaluation and treatment during this COVID-19 pandemic. After obtaining participant's consent, the PI, together with the Telehealth Coordinator, will conduct a selection-consideration review for all participants, to ensure they agree to VVC for training, review clinical "video into home" worksheet and availability of appropriate technology. Participants without appropriate technology will be issued a tablet with web camera and internet access and assisted to create an e-mail account if they do not already have one. All participants who agree to provide a private, conducive environment for in-home training at addresses accessible to EMS, in emergency situations, will be enrolled. At the start of a session, the PI will obtain the address and telephone numbers of participants for use in emergency situations during VVC. Should the need arise, the PI can contact the local medical/telehealth emergency resources for back-up or contact the National Study Participant's Crisis Line for additional help. Before starting the exercise training session, the microphone, speakers and web camera are tested for efficacy in the home for both study participant and PI. The PI will ensure the availability of a telephone backup in the event of a communication failure via VVC. Participants will be advised to be ready 20-30 min prior

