**Pitfalls and Alternatives:** Changes in trabecular bone parameters may be indeterminate because of the smallness and heterogeneity of sample size. We will rely on previous experience to calculate the effect size, and on that basis, adequately power future trials. **Failure to recruit proposed sample size:** The applicant's primary mentor ([name]) successfully conducted similar clinical trials in the past and demonstrated that use of telehealth facilitated recruitment and compliance among Veterans with SCI. Additionally, we may recruit non-Veterans to ensure completion of the study within the proposed timeline. [name] has a dual appointment with VCU and can successfully collaborate with VCU to ensure recruitment of the target sample size.

**Statistical Analyses.** After signing consent, the PI will randomly assign a number from 1-20 to participants using a computer program (nQuery). The order of enrollment will determine the participant's number based on level and duration of injury. Summary of information, including means and SD, frequencies and percentages, for all study variables will be calculated at all-time points. T-tests and Pearson chi-square tests will be used to compare characteristics that may act as confounders, including age, level and time since injury.

**Sample Size Justification:** Being a pilot study, consideration of sample size is just to allow determination and examination of preliminary evidence of efficacy and effect size estimation towards a larger future randomized trial. The proposed sample size of 10 per group is adjudged sufficient to accomplish these goals. Although Julious recommends a sample size of at least 12 per group on the basis that gain in precision for estimates of variance becomes relatively small on reaching a sample size of 12, we are unable to meet that target because of cost of the intervention and testing. Our sample size still allows for adequate accuracy. As shown in **Fig 6**, the gain in precision is still limited with a sample size of 10 per group. Although testing efficacy is not the primary goal, we will have 80% power to detect a standardized mean difference of  $d=0.9$  using an alpha of 0.25 corresponding to a large effect size. Type I error rates larger than 0.05 are often used and recommended for pilot studies where tests of efficacy are not the primary aim.

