### **Common reasons for outpatient visits in fiscal year 2019:**

Reasons for Visit	Number of Veterans
Annual or new evaluation (chronic SCI)	472

The recruitment for the proposed study will be drawn from the SCI population within the Richmond catchment area (this includes Veterans who live outside Richmond but use CVVHCS for their SCI yearly evaluation). After informed consent, each participant will undergo a complete physical examination to be done by the PI or a board-certified Physiatrist. The physical examination will include:

1. General: Race, gender, mood
2. Vital signs:

- a. Temperature
- b. Pulse
- c. Respiration rate
- d. Pulse oximetry
- e. Blood Pressure
- f. Pain level
- g. weight

3. Skin inspection for:
  - a. Rashes
  - b. Eruptions
  - c. Pressure sores
4. Head, Eyes, Ears, Nose, and Throat (HEENT)
  - a. Head-size and shape; tenderness
  - b. Eyes-conjunctiva; sclera, pupil size, shape and reactivity; extraocular muscle movements; visual fields
  - c. Ears-hearing test, tenderness, discharge, external canal, tympanic membrane.
  - d. Nose-symmetry; palpation of sinuses for tenderness; flaring; grunting
  - e. Throat-lips, teeth, gums, tongue, pharynx
5. Neck:
  - a. Range of motion; tenderness, jugular vein distension, lymph nodes, thyroid, carotid bruits, Hepatojugular reflux
6. Chest:
  - a. Symmetry of movement with respiration
  - b. Palpation for tenderness
  - c. Breath sounds
7. Heart:
  - a. Rate
  - b. Palpation of precordium for point of maximal impulse and thrill
  - c. Auscultation for heart murmurs
8. Abdomen:
  - a. Shape
  - b. Auscultation for bowel sounds and bruits
  - c. Percussion for tympanic masses
  - d. Palpate for tenderness/guarding; organomegaly
9. Genitalia:
  - a. Inspect for lesions, swelling, masses, hernias
10. Rectal:
  - a. Inspect/palpate for hemorrhoids, fissures, tags, sphincter tone
  - b. Note presence or absence of stool
  - c. Male- prostate size and texture, nodularity, tenderness
11. Musculoskeletal:
  - a. Range of motion
  - b. Absence of limbs/deformities
  - c. Swelling
  - d. tenderness

12. Neurological assessment:

- a. Mental status
- b. Cranial nerves
- c. motor strength and sensory level based on the International Standards for Neurological Classification of Spinal Cord Injury (ISNCSCI), to determine level of motor and sensory impairment.
- d. Reflexes
- e. Modified Ashworth scale (measure of spasticity)

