- f. Penn Spasm Frequency Scale (self-reported measure of perceived frequency and severity of spasticity).

Eligibility to participate will be based on physical examination findings. Body weight will be measurement using a wheelchair weighing scale and subtracting the wheelchair weight from the total weight to obtain participants' absolute weight. A baseline electrocardiogram (ECG) to rule out any concerning abnormal heart rhythm or myocardial ischemia will be obtained. All participants will also undergo bone mineral density (BMD) measurements using Dual-energy X-ray absorptiometry (**DXA**) focusing on the distal femur and proximal tibia and MRI using a 3 Tesla magnet (GE) to determine skeletal muscle and cortical bone CSAs (specific Aim 1) and fasting blood work (specific Aim 2), at no cost.

**Inclusion criteria.** To be included, participants will have to:

1. Be 18-65 years of age
2. Have history of traumatic SCI ( $\geq$ 1-year) with NLI of C8-T10 and AIS A or B (confirmed by AIS examination performed by PI or a qualified Provider).
3. Have a caregiver who is available and willing to be trained to apply intervention protocol in the home (placing weights and positioning the Veteran) throughout study duration
4. Be a wheelchair user for primary mode of mobility
5. Have Knee extensors that must respond to standard surface electrical stimulation procedures (stimulation frequency procedures, 30 Hz; pulse duration:1 ms and amplitude of the current of less than200 mA)).
6. Be able to receive written clearance from their medical Providers to ensure safety of participants.
7. **Be a Veteran (male or female),** however, the Department of Veteran Affairs has limited number of female Veterans, especially those with motor complete injury at level C8-T10 (currently, there are only 3 female Veterans with the target NLI in our SCI registry). Hence, inclusion of women Veterans may be challenging due to this disparity in the SCI population. If we fail to recruit 20 Veterans, we may seek an IRB approval to recruit non-Veterans to meet our target sample size.
8. Have normal ECG
9. Commit to undergo 9 months of trial; 4.5 months of open-kinematic chain resistance training followed by 4.5 months of closed-kinematic chain using simple rowing approach + Vit. D supplementation (Experimental group) **or** 9 months of passive movement +Vit D supplementation (control group).

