**Detailed Strategies for the Recruitment Plan.**

Efforts will be made by the applicant (PI), to implement a successful recruitment plan, and to avoid any source of coercion during the actual process. Twenty Veterans (10 in

intervention group vs. 10 in control group) with motor complete SCI involving C8-T10 and AIS A or B classification, will be recruited to participate in a 9 months trial. The primary goal of this work is to ensure that our procedures are safe and effective for persons with motor complete SCI.

The following timeline will be implemented to meet our recruitment goals. We plan to recruit 20 Veterans/non-Veterans over a 2-year period (24 months). We plan to start participants enrollment in the 1st quarter of year-1 and finish in 1st quarter of year-2 (see recruitment table below). We will continue to collect data and finish analysis by the 4th quarter of year two. This is feasible considering our previous experience recruiting for the parent study. Also, we do not anticipate attrition due to prior established compliance with telehealth home-based study. We plan to offer resistant training to participants on a flexible schedule so as to accommodate their lifestyle, to avoid attrition. Participants will be randomized to either intervention or control group.

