## Process for obtaining informed consent:

The PI will seek informed consent from eligible participants with an IRB approved consent form. Determination of a participant's capacity to consent will be made by the PI. Input may be solicited from participant's SCI Provider on record, who knows the potential participant well. Potential participants will be given full verbal explanation of the study protocol by the PI. If they voice an interest in the study, they will receive the written consent form and will be provided ample time to consider their participation. All concerns and questions will be answered by the PI. The PI will place emphasis on explaining all study procedures. Family members will be included in the discussion as desired by the participants. Participants will be made aware that participation is voluntary and that they can withdraw at any time with no impact on the care they currently receive or future care from the VA. Participants will be made aware that they can discuss the study participation with their primary SCI Provider, if they chose. Potential participants who take the consent forms home will be given a returned addressed envelope with postage paid in which they can mail back the consent form once signed. All signed consents will be scanned into the VA Computerized Patient Record System (CPRS); a warning note indicating participation in an ongoing research study will be enter in the "Crisis Notes, Warning Notes, Directives (CWD)," section of CPRS to alert CPRS users of participants' enrollment in an ongoing study. In addition to a consent note entered into CPRS for all participants, progress notes of their active participation will also be entered.

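### The only allocation rule contradicts itself, links no number to an arm and describes no concealment, while the principal investigator who issues the number also has a say in who enters

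*Combined protocol and SAP*

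**What the plan says.** Allocation is described in two adjacent sentences under Statistical Analyses. The first reads "After signing consent, the PI will randomly assign a number from 1-20 to participants using a computer program (nQuery". The second reads "The order of enrollment will determine the participant's number based on level and duration of injury". The recruitment plan adds only "Participants will be randomized to either intervention or control group", with a target of 10 per arm, and Research Design and Methods calls the study a randomised controlled trial. Neither gives a method.

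On who decides entry:

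- Under Process for obtaining informed consent: "The PI will seek informed consent from eligible participants with an IRB approved consent form".
- Under Human Subjects Involvement and Characteristics: "After informed consent, each participant will undergo a complete physical examination to be done by the PI or a board-certified Physiatrist", followed by "Eligibility to participate will be based on physical examination findings".
- Item 18 of the exclusion criteria in the Human Subject Section lets the PI or another provider exclude on judgment.
- Under Home Video Telehealth Service, after consent, "the PI, together with the Telehealth Coordinator, will conduct a selection-consideration review for all participants". The same section says "All participants who agree to provide a private, conducive environment for in-home training at addresses accessible to EMS, in emergency situations, will be enrolled".

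**The concern.** A number cannot be drawn at random and also be fixed by the order of enrolment or by features of the injury, unless some further rule joins the two. None is given. Nor does the plan say which numbers go to which arm, so the step that turns a number into a treatment is missing.

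Randomisation protects the comparison only if the person who decides whether and when someone enters cannot know or influence the next assignment. Here that person may be the one issuing the assignment. If entry were steered, even without intent, the arms could differ in ways that the planned comparison of age, injury level and time since injury would not show. The baseline-adjusted analysis would remove only the part that the baseline score predicts. The sample-size section says the pilot is to give preliminary evidence of efficacy and an effect size for a larger randomised trial, so any such bias would pass into that trial's design.

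**Working it through.** **1. The two sentences side by side.** Three readings are possible.

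- *The number is drawn at random when each person consents.* Then enrolment order and injury features do not determine it, and the second sentence is wrong.
- *The number follows enrolment order.* Then it is not random, and any randomness must lie in a key from number to arm. No key is given.
- *A random list is made in advance and used in enrolment order, stratified by injury.* This is the kindest reading. It needs named strata, cut-points for level and duration, a list for each stratum, a key to arms and a holder for the lists. None of these is stated.

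**2. Is the missing step elsewhere?** The design statement, the recruitment plan and the sample-size paragraph give the word randomised and the target of 10 per arm, but no sequence, block, stratum, key or concealment. The only mention of double blinding concerns a cited vitamin D study. The two sentences are complete and adjacent, so nothing suggests that redaction explains the gap.

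**3. Roles.**

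| Step | Who | Where |
|---|---|---|
| Issues the number | PI | Statistical Analyses |
| Seeks consent | PI | Process for obtaining informed consent |
| Examination that decides eligibility | PI or another physician | Human Subjects Involvement and Characteristics; Study Procedures |
| Exclusion on judgment | PI or other providers | Exclusion criteria, item 18 |
| Supervises resistance training | PI, by telehealth | Resistance training (RT) |
| Supervises rowing progression | Trained caregiver | Resistance training (RT), rowing phase |

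The training rows come after assignment. They matter here for one reason: the PI learns past assignments.

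**4. Order of events.** The number is issued after consent. The eligibility examination also follows consent. The Home Video Telehealth section places its review before enrolment, and Protection against risk of fracture places the DXA scan before enrolment. These suggest consent, screening, enrolment, number. The allocation sentence itself requires only that consent has been signed.

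**5. What can be calculated.** The plan states no figure for allocation. Its nearby power statement (10 per arm, d = 0.9, alpha 0.25, 80%) reproduces: a two-sided t-test with 18 degrees of freedom gives 79.6%, and the normal approximation 80.6%. That figure does not depend on this point.

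Two quantities bear on the fix.

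- *Guessability of a fixed 10:10 list.* Someone who knows past assignments and always guesses the arm with more places left is right on average 10 + ½ × (4^10 / C(20,10) − 1) times. With 4^10 = 1,048,576 and C(20,10) = 184,756, this is 10 + ½ × (5.675 − 1) = 12.3 of 20, against 10 by chance. Someone holding the list knows all 20.
- *Separate unblocked lists by stratum.* Suppose there are two strata, each with its own 10:10 list of 20 places, and each enrols 10. The number in one arm is the sum of two hypergeometric counts (10 drawn from 20, of which 10 belong to that arm). The chance of 12/8 or worse overall is 35%.

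**The case against.** The strongest reply is that silence is not absence. Numbers as written have no arms, so the text alone lets nobody foresee anything. A number drawn by software at the moment of assignment is not foreseeable. Foresight needs two things the plan does not state: that the PI holds the key, and that numbers run in a known order. This stands. A reader might infer that the plan makes the next arm foreseeable, or that there will be no independent list-holder. The documents support neither; they show only that foresight is not excluded.

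Second, the order of events is not wholly open. The sections on telehealth review and DXA point to screening before enrolment, and the second allocation sentence ties the number to enrolment. This also stands in part: the natural reading is sound, but the wording does not secure it.

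Third, the PI's control of entry is not complete. Another physician may examine, the telehealth review is shared with a coordinator and concerns video, technology and emergency access, and most eligibility criteria are objective thresholds. This limits the opportunity for steering but does not remove it, because consent, its timing and judgment exclusions remain.

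Fourth, this is a pilot whose primary analyses are mainly descriptive. That lowers the stakes of a test, but not of the effect estimate that is to be carried forward.

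A reader might also want a figure for the bias. With k steered pairs whose expected outcomes differ by D standard deviations, the shift with 10 per arm is kD/10; one pair 1 SD apart gives 0.1 SD, against a sampling error of about √(2/10) = 0.45 SD. Both k and D would be invented, since the documents give no steering rate, so such a figure carries no weight here.

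**Conclusion.** The point holds in this form. The only allocation rule contradicts itself, has no link from number to arm, names no strata and describes no concealment. It places assignment with a PI who also seeks consent and may judge eligibility. It does not rule out assignment before eligibility is settled. Two teams could run different allocations, one of them predictable, and both could claim to follow the plan.

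This is a defect in what the text permits, not evidence that allocation will be steered. No size can be given for the resulting bias. The conclusion rests on the wording and the roles, not on any assumed rate. It should be corrected before enrolment, because allocation cannot be repaired afterwards.

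**What to change.** Replace both allocation sentences under Statistical Analyses with a single method, for example:

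> A computer-generated 1:1 list linking each number to an arm is prepared and held by an existing staff member or statistician not involved in consent, eligibility or training. Each assignment is released one at a time, only after eligibility is confirmed and baseline tests are complete.

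Keep no wording that ties the number to injury level or duration, unless balance on it is intended. If it is, name one two-level stratum. Use a concealed list for each level, in small blocks of randomly varying size that the PI does not know, because unblocked lists risk the imbalance shown above. Include the stratum in the ANCOVA.

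The cost is protocol wording and a short task for one existing person. Stratifying takes one residual degree of freedom: with 20 participants, 20 − 3 = 17 (intercept, arm, baseline) becomes 16. It may also leave small departures from 10:10.

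One weakness remains. Because the PI supervises resistance training and so learns past assignments, a fixed 10:10 total stays partly guessable even with a concealed list (about 12.3 of 20), and the last assignment is always known. The plan should acknowledge this.

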## Human Subject Section:

## **I. Human Subjects Involvement and Characteristics:**

Twenty (20) individuals with chronic (>1-year post-injury), motor complete Spinal Cord Injury (SCI) with American Spinal Injury Association Impairment Scale (AIS) score A or B will be recruited to participate in the proposed Telehealth study. Participants will be recruited from the Central Virginia VA Health Care System (CVVHCS) Spinal Cord Injury & Disorders (SCI&D) registry. The SCI&D registry has approximately 1,800 Veterans (men and women), with more than 298 of the Veterans meeting the criteria for neurological level of injury (NLI) of C8-T10 and AIS A or B, which is our target study population. The SCI population is however, predominantly male based on natural disposition, since men tend to join the military than do women.

The SCI service at CVVHCS offers inpatient and outpatient services. The inpatient service provides acute rehabilitation services for Veterans with new SCI, annual evaluation for those with motor complete injury who are unable to use outpatient level of care, Veterans with pressure ulcers that are not responding to outpatient level of care and those requiring respite care to relieve caregivers of care burden. Veterans needing minor surgical procedures are also admitted for short inpatient stay, for example, for cystoscopy or colonoscopy procedures. In 2019 fiscal year, there were a total of 1022 Veterans, ages 18 to 70 years, within the Richmond catchment area and 298 reside in Richmond. Over 800 were admitted to SCI inpatient service for various reasons and over 600 Veterans used outpatient level of care. The tables below show some of the common reasons for inpatient and outpatient care, by number of Veterans, for fiscal year 2019:

